According to amendment 2, the final market image version 3 (FMI III) formulation of BGJ398 replaced FMI I. These two formulations have been previously compared in two separate studies [CBGJ398X2103 and CBGJ398X2106] to the clinical service form which was used to establish MTD of BGJ398 at 125 mg qd [CBGJ398X2101]. Crossstudy comparison of the exposures (AUC and Cmax) between FMI III and FMI I indicated that exposure of BGJ398 from the FMI III formulation is about 21-35% higher than that of FMI I (21% for AUCinf, 29% for Cmax and 35% for AUClast). Although BGJ398 has demonstrated high interpatient variability in exposure at the 125 mg dose, on average, steady-state concentrations provide target coverage over the dosing interval at doses associated with efficacy. As observed events with BGJ398 are readily monitorable and considered manageable, patient's doses can be individually titrated to maximize therapeutic potential and minimize toxicity across a wide exposure range. Thus, the dose of FMI III 125 mg qd should pose no additional safety concerns. However, pharmacokinetics, safety and tolerability data from the first 20 patients treated with FMI III up to the end of cycle 1 of treatment will be assessed and compared with the historical data from patients treated with FMI I. Upon review of the data, it may be decided to continue dosing all subsequent patients at 125mg or at a lower dose. All decisions will be made by the QED Therapeutics study team in conjunction with the Investigators. Serial blood samples will also be collected from the remaining patients in this study to further characterize the pharmacokinetic properties of FMI III in this patient population.

According to amendment 4, the final market image version 4 (FMI IV) formulation of BGJ398 will be used for patients in Cohorts 2 and 3. Additionally, patients in Cohort 1 will be transitioned for FMI IV when this formulation is available at the study site. Pharmacokinetics, safety, and tolerability data from all available patients in Cohorts 2

and 3 treated with FMI IV up to the end of cycle 1 of treatment will be assessed and compared with the historical data from patients treated with FMI III.

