## 6.1.1.1 Instructions for administration of BGJ398

- Patients should be instructed to take the daily dose of BGJ398 in the morning, at approximately the same time each day (24 ± 4 hour interval). Patients will take their first dose of infigratinib at the study center on Cycle 1 Day 1. On the days of PK sampling, patients should not take their study drug dose at home; patients should take their study drug with them to the investigative site where administration of BGJ398 will be supervised and administration time recorded. On PK sampling days after Cycle 1 Day 1, the time of the previous infigratinib administration (ie, the prior day) before the pre-dose PK sample will be recorded in the eCRF. Administration may fall outside of the ±4 hour interval on the days of PK sampling.
- Patients who initiate treatment as of the implementation of amendment 2 will begin treatment using the FMI III form of BGJ398; patients enrolled into Cohorts 2 and 3 under amendment 4 will receive the FMI IV form of BGJ398. Patients who started treatment prior to the implementation of amendment 2 should continue to receive the formulation of BGJ398 that they received at the initiation of treatment until FMI IV is available at the study site. At that time all patients on study will receive FMI IV.
- BGJ398 should be administered in the fasted state at least 1 hour before or 2 hours after a meal.
- BGJ398 should be taken with a large glass of water (~250 mL) and consumed over as short a time as possible. Patients should be instructed to swallow the capsules whole and not chew them.
- If the patient forgets to take the scheduled dose in the morning (other than on a day of PK sampling), he/she should not take the dose more than 4 hours after the usual time and should continue treatment the next day. Any such doses that are missed should be skipped altogether and should not be replaced or made up at the next scheduled dosing.
- If vomiting occurs following the dosing of study drug, re-dosing is not permitted that same day. Dosing should resume the next day. If the vomiting occurs on full PK sampling days within the first 4 hours post-dosing, this event needs to be noted on the dose administration PK eCRF page, as well as on the adverse event page, as appropriate.

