#### 6.5 Study drug preparation and dispensation

The investigator or responsible site personnel must instruct the patient or caregiver to take the study drugs as per the protocol. Study drug(s) will be dispensed to the patient by authorized site personnel only. All dosages prescribed to the patient and all dose changes during the study must be recorded on the Dosage Administration Record CRF.

BGJ398 will be supplied as hard gelatin capsules for oral use at dose strengths of 25 and 100 mg. Excipients will include microcrystalline cellulose, lactose monohydrate, hypromellose 2910, crospovidone, colloidal silicon dioxide, magnesium stearate, and hard gelatin capsule. BGJ398 will be manufactured under Good Manufacturing Practice for investigational use. The color and appearance of the capsules are outlined below.

Final market image version 3 (FMI III) formulation (Cohort 1):

Physical	Size 3 Capsule: Swedish orange opaque cap and body filled with white to greyish powder (25 mg)
Attribute	Size 1 Capsule: Swedish orange opaque cap and body filled with white to greyish powder (100 mg)

Final market image version 4 (FMI IV) formulation (all cohorts):

Physical Attribute	Appearance (color)	Size 3 Capsule: White opaque body with gray opaque cap, imprinted with a green band on the body and a black band on the cap filled with white to greyish powder (25 mg)  Size 1 Capsule: White opaque body with light orange opaque cap, imprinted with a green band on the body and a black band on the cap filled with white to greyish powder (100 mg)
-----------------------	--------------------	---

The FMI III formulation will be provided in 28-count bottles, and the FMI IV formulation will be provided in 21-count bottles.

Patients who initially received FMI III will be switched over to FMI IV when FMI IV is available at the study site.

The site pharmacist or designee will dispense the correct number and dose strength of capsules to ensure the patient receives sufficient drug for each 28-day treatment cycle. Study drug will be dispensed to the patient by authorized trained site personnel only.

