2 STATISTICAL METHODS

2.1 Data Analysis General Information

Study data will be analyzed by QED Therapeutics and/or designated CRO(s) using the most updated SAS® version in the statistical computing environment. PK parameters will be calculated using non-compartmental methods available in Phoenix WinNonlin version 7.0 or higher.

Two formal interim analyses for Cohort 1 are planned after Amendment 3 as described in Section 2.9. The first formal interim analysis will include all patients in Cohort 1 who receive study treatment before the interim analysis cutoff date. The efficacy analysis for the first formal interim analysis for Cohort 1 will be focused on the population as described in Section 2.2.2 below. The second formal interim analysis will be conducted on all the subjects with FGFR2 fusions or translocations in Cohort 1. The primary analysis for Cohort 1 will be conducted when all patients in Cohort 1 have the potential to be followed for at least 10 months after their initial exposure to study treatment. For the interim and primary analyses for Cohort 1, patients will be grouped by fusion status (if subjects without FGFR2 fusions or translocations are included) and formulation. Here, the formulation refers to the first formulation a subject received if a subject switched formulation during the study as described in Section 1.1.

For Cohorts 2 and 3, review of data will be performed after a total of 15 patients in either Cohort 2 or 3 have been treated with FMI IV for at least one cycle. Primary analysis will be conducted when all patients in the cohorts have the potential to be followed for at least 10 months after their initial exposure to study treatment. Additionally, for Cohort 3, one interim analysis will be conducted after the first 10 dosed patients in this cohort have the potential to complete their second scheduled scans (approximately 16 weeks from their first dose) to determine if the cohort will be expanded.

The additional data for patients continuing to receive study treatment or remain in study past the data cutoff date of the primary analysis, as allowed by the protocol, will be reported in a final CSR that will be prepared at the end of the study. In the final CSR, analyses will be done for each cohort, for patients enrolled in Cohort 1 who do not have FGFR2 fusions or translocations, data may be combined and summarized with Cohort 2.

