2.1.1 General Definitions

2.1.1.1 Investigational Drug and Study Treatment

Investigational drug will refer to infirgratinib as an oral formulation. The terms investigational drug and study drug/treatment are used interchangeably. For consistency across studies, the term study treatment will be used throughout this document.

Table 3: Dose and Treatment Schedule

| Study treatment | Formulation | Pharmaceutical form and route of administration | Dose | Frequency and/or Regimen |
|-----------------|-------------|---|---|--|
| infirgratinib | FMI I | Capsule(s) for oral use | 125 mg (administered as one 100 mg capsule and one 25 mg capsule) | Daily (3 weeks on, 1 week off schedule in 28-day cycles) |
| | FMI III | | | |
| | FMI IV | | | |

A **treatment** is defined by the dose formulation (FMI I, FMI III and FMI IV). The treatment formulation is determined by the formulation a subject first received if a subject switches formulation during the study as described in Section 1.1.

Unless otherwise specified, all efficacy related analyses will be done separately for all patients, patients with baseline FGFR2 gene fusion/translocation, and patients with other FGFR genomic

alterations if subjects without FGFR2 fusion/translocation are included in the analysis. In addition, within patients who had baseline FGFR2 gene fusion/translocation, the data will be summarized by treatment. Unless otherwise specified, for all other analyses, including safety, disposition, demographic/baseline disease characteristics, study drug exposure and prior/concomitant/post therapy related analyses, will be done separately for all subjects, all subjects by FGFR status (FGFR2 gene fusion/translocation vs. other FGFR genomic alterations) if subjects without FGFR2 fusion/translocation are included in the analysis, and all subjects by treatment.

Note that reporting by treatment is equivalent to reporting by formulation, and “by treatment” will be used throughout this document.

2.1.1.2 *Date of First/Last Administration of Study Treatment*

In the single agent arm, the date of first (last) administration of study treatment is derived as the first (last) date when a non-zero dose of infigratinib was administered and recorded on the Dosage Administration Record (DAR) eCRF. If a subject has not ended treatment at data cut-off date for an analysis, the subject is considered ongoing at the last dosing record.

2.1.1.3 *Study Day*

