2.7.2.1.2 Data Analysis

AE Summaries

AE summaries will include all AEs occurring during on-treatment period, i.e. treatment emergent AEs. Treatment emergent AEs (TEAEs) include all AEs that started on or after the first administration day of study treatment and up to last study administration day of study treatment +30 days. All AEs collected in the AE (e)CRF page will be listed along with the information collected on those AEs, eg, AE relationship to study drug, AE outcome, etc. Treatment-emergent AEs will be flagged in the listings.

TEAEs will be summarized by number and percentage of subjects having at least one TEAE, having at least one TEAE in each primary system organ class (SOC) and for each preferred term (PT) using MedDRA coding. A subject with multiple occurrences of an AE will be counted only once in the respective AE category. A subject with multiple CTCAE grades for the same preferred term will be summarized under the maximum CTCAE grade recorded for the event. AE with missing CTCAE grade will be included in the 'All grades' column of the summary tables.

In TEAE summaries the primary system organ class will be presented alphabetically, and the preferred terms will be sorted within primary SOC in descending frequency. The sort order for the preferred term will be based on their frequency in FAS. The following TEAE summaries will be produced by treatment and by FGFR2 fusion/translocation status:

- Overview of TEAEs and deaths (number and % of subjects who died from fatal TEAE, number and % of subjects with any TEAE, any treatment emergent serious AE, any TEAE leading to dose reductions/interruptions, TEAE leading to discontinuation of study treatment)
- All TEAEs by SOC and PT and worst grade
- Treatment related TEAEs by SOC and PT and worst grade
- Grade 3 or 4 TEAEs by SOC and PT and worst grade
- Treatment emergent serious AEs (SAEs) by SOC and PT and worst grade
- Treatment emergent serious treatment-related AEs by SOC and PT and worst grade
- TEAE with fatal outcome by SOC and PT and worst grade
- TEAE leading to study treatment discontinuation by SOC, PT and grade
- TEAE leading to dose interruption/adjustment by SOC, PT and grade
- TEAE leading to treatment discontinuation by SOC and PT and worst grade
- TEAE requiring additional medication or therapies by SOC and PT and worst grade
- All TEAEs by PT by descending order of frequency
- Treatment related TEAEs by PT by descending order of frequency

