PK data generated from this study may be used in conjunction with PK data from other clinical studies for population PK and PK/PD assessment. These assessments will be reported separately. If possible, exploratory comparisons will be made to historical pharmacokinetic data. Available PK data from this study may be modeled using a population pharmacokinetic data analysis approach in order to characterize the population pharmacokinetics of infigratinib. Any population PK data generated will be reported separate from the CSR.

All analyses will refer to infigratinib and its metabolites. Infigratinib and its metabolites concentration vs time data will be reported.

Analysis will be done separately for the three formulations. In addition, analyses that require derived PK parameters will be applicable to subjects treated with FMI III and FMI IV who have provided PK parameters based on extensive PK sampling as indicated in Table 11 of [CSP Amendment 5](#).

2.7.4.3 *Analysis Sets*

Only PK blood samples with the date and time and for which the last prior dose dates and times are adequately recorded will be included in the PK analyses. Samples taken from patients who vomited within 4 hours of dosing will be excluded from the analysis. The PAS will be used.

2.7.4.4 *Basic Tables, Figures, and Listings*

The PK concentration and PK parameters (when available for subjects treated with FMI III or FMI IV), will be summarized and listed using relevant statistics by treatment, and study day. Descriptive statistics (mean, SD, CV%, geometric mean, geometric CV%, median, and range) will be presented. Median, minimum and maximum will be calculated based on collected samples. When a geometric mean is presented, it will be stated as such. Only median values and ranges will be presented for T_{max} .

Graphical plots of individual and mean plasma concentration-time data will be generated for infigratinib and its metabolites. This graphical presentation will be applicable to subjects who are treated with FMI III and have PK profile collected as per Table 11 of [CSP Amendment 5](#). Further graphical exploratory analysis will be carried out if deemed appropriate.

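### Cohort 1 safety and dose-change tables by formulation report events that start on FMI IV under FMI I or FMI III, because patients stay classified by the first formulation they received

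*SAP*

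**What the plan says.** **The grouping rule.** SAP 2.1.1.1 defines treatment as formulation, "determined by the formulation a subject first received if a subject switches formulation during the study", and treats reporting by treatment and by formulation as the same thing. SAP 2.1 repeats the rule for the Cohort 1 interim and primary analyses: "the formulation refers to the first formulation a subject received if a subject switched formulation during the study".

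**The switch.** It is planned, and it applies to everyone still on drug. Protocol 2.3: "patients in Cohort 1 will be transitioned for FMI IV when this formulation is available at the study site". Protocol 6.1.1.1, on the arrival of FMI IV at a site: "At that time all patients on study will receive FMI IV". Protocol 6.5: "Patients who initially received FMI III will be switched over to FMI IV when FMI IV is available at the study site".

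**The tables that use the rule.**
- Adverse events (SAP 2.7.2.1.2): "The following TEAE summaries will be produced by treatment and by FGFR2 fusion/translocation status".
- Dose reductions and interruptions, with reasons, by treatment (SAP 2.5.1.1).
- Study drug exposure by treatment (SAP 2.1.1.1).
- Phosphate-binder use by formulation and, among users, Grade 3/4 hypophosphatemia (SAP 2.7.2.1.2).
- PK concentrations (SAP 2.7.4.4): "will be summarized and listed using relevant statistics by treatment, and study day".

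**The observation window.** SAP 2.1.1.5 runs the on-treatment period from the first dose to 30 days after the last dose of any study treatment. A change of formulation does not end it.

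**The concern.** Put together, these rules credit everything that happens after the switch to a product the patient is no longer taking. A Cohort 1 patient who starts FMI III, moves to FMI IV and then has a first Grade 3 event, or a first dose reduction, is counted under FMI III. That patient's time on FMI IV is also counted as FMI III exposure.

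The by-formulation columns exist to show how each product was tolerated. As planned, the Cohort 1 FMI III column mixes two products, and Cohort 1 experience on FMI IV appears in no FMI IV column. SAP 2.2.1 plans summaries by all three formulations, yet with first formulation as the label the Cohort 1 FMI IV column will be empty or nearly so, although Cohort 1 patients take FMI IV.

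The SAP's cross-reference adds to the problem. The rule points to SAP 1.1 for a description of switching, but SAP 1.1 describes it only for patients who started before Amendment 2. The move from FMI III to FMI IV, which involves more patients, is not mentioned there.

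**Working it through.** The plan states no figure for this, so there is nothing to reproduce. The first step is a reading of the text. The second gives a rough size under stated assumptions. The third separates what is affected from what is not.

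**Step 1. Does anything offset the rule?** Neither document attributes events by formulation at onset, censors at the switch, or plans a sensitivity analysis by formulation actually taken. Protocol 10 asks for subanalyses by formulation as appropriate but gives no attribution rule. The misattribution in the safety and dose-change tables therefore follows from the text alone.

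**Step 2. How many patients might switch?** The documents give neither accrual dates nor switch dates.

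Inputs:
- Amendment 2, which brought in FMI III: 24 January 2017.
- Amendment 4, which brought in FMI IV: 24 April 2019, so T = 820 days later.
- Median PFS of 175 days (95% CI 130 to 230) in the first 61 patients (protocol, Amendment 2 rationale), used in place of time on drug.

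Assumptions: exponential time on drug with median m; FMI III accrual uniform over T and then closed; FMI IV reaching sites L days after Amendment 4.

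*FMI III starters.* The share still on drug at the switch is the average of 0.5^(x/m) for x from 0 to T, times 0.5^(L/m):

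share = [m / (T ln 2)] × [1 − 0.5^(T/m)] × 0.5^(L/m)

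For m = 175 and L = 0: 175 / (820 × 0.693) × (1 − 0.039) = 0.308 × 0.961 = 0.296.

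| Median (days) | L = 0 | L = 183 | L = 365 |
|---|---|---|---|
| 130 | 23% | 9% | 3% |
| 175 | 30% | 14% | 7% |
| 230 | 37% | 21% | 12% |

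If accrual continued after Amendment 4, these shares would be higher.

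A rough head count follows. Cohort 1 is about 120 patients, 61 of them enrolled at the June 2016 review, which leaves at most about 59 FMI III starters. From the other side, 106 − 72 = 34 fusion patients lie outside Interim Efficacy Analysis Set 1, and adding about 20 extensive-PK patients gives about 54. At m = 175 that is about 4 patients (0.070 × 54) to 17 (0.296 × 59).

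*FMI I starters.* Taking them all to have started by Amendment 2, the share still on drug at Amendment 4 is at most 0.5^(820/175) = 3.9% (1.3% to 8.4% for medians of 130 to 230 days), or about 2 of 61 (1 to 5).

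**Step 3. Which PK data are exposed?**
- *Derived parameters.* They come only from Cycle 1 Day 1 and Day 15 profiles (Protocol 10.5.3, SAP 2.7.4). The FMI III profiles come from about 20 patients, the first treated with it. FMI IV profiles come from Cohorts 2 and 3, which start on FMI IV. The rule does not touch these.
- *FMI I concentrations.* The note to protocol Table 10 says sparse-sampling patients enrolled before Amendment 4 had no Cycle 4 to 6 samples. Their schedule ends at Cycle 3 Day 1, day 57 (day 71 if the Cycle 3 Day 15 trough is counted). FMI I starters were past that long before FMI IV existed in the study, so only an unscheduled sample could follow the switch.
- *FMI III concentrations.* A sparse-sampling patient who switches while samples are still due can be mislabelled: through Cycle 3 if enrolled before Amendment 4, through Cycle 6 Day 15 (day 155) if enrolled under it. The extensive group also has Day 1 troughs to Cycle 6 (day 141), but as the first FMI III starters they are the least likely to have had one due after April 2019.

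**The case against.** The best defence is that the rule is openly prespecified and has a purpose. A group fixed at the start is not selected on later survival, whereas a post-switch column contains only patients who stayed on drug long enough to switch. The Cohort 1 safety objective is the type, frequency and severity of events, not a contrast between formulations, and the all-subject tables answer it. This stands, and it is a good reason to keep first formulation for efficacy. It does not justify safety columns labelled with a product the patient had stopped taking.

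A reader might infer more than the documents support:

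- *That the PK characterisation of FMI III and FMI IV is compromised.* Step 3 shows that the parameters are not. What remains is a limited set of later FMI III concentrations, and SAP 2.7.4 leaves further detail to a separate PK analysis plan, which may settle them.
- *That the rule confounds formulation with cohort.* That comes from the design: FMI IV starters are Cohorts 2 and 3, and the planned comparison sets their Cycle 1 data against historical FMI III data. Relabelling Cohort 1 events would not change it.
- *That formulation differences will look smaller.* The direction is not established. A patient counts once per event category at maximum grade, so extra time after the switch can raise the FMI III incidence. The protocol's statement that "exposure of BGJ398 from the FMI III formulation is about 21-35% higher than that of FMI I" concerns a different pair; neither document gives an exposure difference for FMI IV.

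The size estimate is also open to attack. PFS stands in for time on drug, and it comes from early FMI I patients who were not all fusion-positive. It counts patients still on drug, not misattributed events: an event that began before the switch and did not worsen afterwards is labelled correctly.

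**Conclusion.** The point holds for the Cohort 1 by-formulation summaries of adverse events, dose reductions and interruptions, exposure, and phosphate binders with hypophosphatemia. For these it rests on the text and needs no assumption. The FMI III column carries most of the error.

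Its size is uncertain. With a 175-day median, roughly 7% of FMI III starters (FMI IV at sites 12 months after Amendment 4) to 30% (immediate availability) would still be on drug at the switch. This depends on uniform accrual that ends at Amendment 4 and on exponential time on drug; later accrual would raise it. For FMI I starters the share is about 4% or less at the same median.

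The primary response rate, the all-subject safety tables, the Cycle 1 Day 1 and Day 15 PK parameters and the scheduled FMI I samples do not change. In PK, the practical exposure is limited to later concentrations from FMI III sparse-sampling patients who switch while samples are due, subject to the separate PK plan. This is an inexpensive improvement that should be made; it does not threaten the trial's main conclusion.

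**What to change.** 1. In SAP 2.1.1.1, keep first formulation for efficacy. For Cohort 1 by-formulation safety, dose-change and exposure summaries, end the FMI I or FMI III period at the first FMI IV dose. Show later events and exposure in a separate column, such as Cohort 1 after switch to FMI IV, with its own exposure time and labelled descriptive. Apply the same split to the phosphate-binder and hypophosphatemia summary.
2. In SAP 2.7.4, state that each PK concentration is grouped by the formulation of the last dose before the sample.
3. In SAP 1.1, describe the FMI III to FMI IV switch so that the cross-reference in the rule is complete.

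The cost is wording and programming, plus recovery of switch dates. The protocol requires dosing records and a dispensing log but does not say that formulation is captured in the eCRF, so this should be checked first. The two products differ in capsule appearance and bottle count (28 against 21), which should help identify them in dispensing records. The downside is that the post-switch column will be small and made up of patients who stayed on drug long enough to switch, so it should not be used for a formal comparison of formulations.
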